9.1.3 Visit 3 – Day +1

During this visit, the following assessments or tasks will be performed:

- Use/change of **concomitant treatments** will be documented;
- **Blood samples for baseline haematology/biochemistry tests** will be collected according to central laboratory manual;
- **Vital Signs** (systolic and diastolic Blood Pressure in supine position, PR) should be recorded;
- **Injection-site tolerance** is to be evaluated;
- **Assessment of AEs** will be documented;
- **Proposed diagnosis as standard of reference** for each nodule (HCC, other malignant, regenerative or dysplastic nodule, benign, uncertain) should be assessed according to available evaluations (excluding histology and P03277 images) .

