- **Hematology tests** by central lab at screening visit or inclusion visit and after administration at Day+1 for all subjects : Red Blood Cells (RBCs), White Blood Cells (WBCs), neutrophils, eosinophils, basophils, lymphocytes and monocytes, platelet count, hemoglobin, hematocrit, Mean red blood Cells Volume (MCV).
- **Tolerance at the injection site** will be recorded from time of administration of P03277 up to 30 minutes post administration and 1 day after injection.
- **Adverse event (AE)** will be recorded throughout the subject participation until the +1day safety FU. Only AE that the investigator considers as related to P03277 and/or the study procedures will be recorded at the optional Visit 4 between 3 days after P03277 administration up to 3 month.

Statistical methods:

For primary endpoint: descriptive analysis of P03277 MRI sensitivity and specificity results using standard of reference will be presented by dose.

Descriptive statistics will be provided for secondary efficacy endpoints will be presented by dose and clinical and biological safety and will presented by dose and overall.

 CONFIDENTIAL	Protocol No. GDX-44-008 Version No.4.0 including amendments 1 and 2 12 December 2017	Page 7 / 64
---	--	-------------

STUDY FLOW CHART

[figure not shown]
Visit	Screening (V1)	Inclusion and P03277 liver imaging visit (V2)					Safety follow-up (V3)	Biopsy /procedure for specimen histology (V4 optional as per standard of care)	
Timing	-7 to -0 days	Inclusion Day 0	Pre-injection	Dosing	Acquisition of triphasic MRI sequences	30mn	Optional very delayed acquisition	Day +1	Between 3 days after V2 and up to 13 weeks
Informed consent signature	x								
Eligibility criteria (1)	x	x							
Physical examination (2)	x								
Demographic data	x								
Medical history	x								
Chronic liver disease status	x								
Previous imaging results and AFP measurement collected for reference diagnosis	x	x							
Proposed diagnosis according to available examinations for standard reference (excluding histology and P03277 images)								x	
Biopsy histologic analysis for reference diagnosis (3)									x
Body weight		x							
Concomitant treatments	↔								
Pregnancy test (4)	x	x							
Vital signs (BP, HR) (5)	x	x				x		x	
Blood samples for laboratory parameters (6)	(x)	x						x	
e-GFR for screening (7)	x								
IP administration			x						
MRI examination (8)			x	x		(x)			
Injection-site tolerance (9)					↔		x		
Adverse events (AEs) (10)	↔								(x)

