6.3 Prohibited Concomitant Treatments

Any other contrast agent should not be administered with 7 days before and 3 days after P03277 administration.

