7.2 Secondary Criteria

7.2.1 Efficacy assessments of P03277 imaging

- **Technical adequacy of images** (*ongoing on-site and expert reading*) will be assessed as adequate, yes or no and reason for inadequacy will be recorded using-a 5 items (1= Artifacts due to subject , 2 = Artifacts due to machine, 3 = Artifacts due to contrast agent, 4 = Injection technical failure, 5 = Other, specify)
- **Visualization of biliary and liver vascular abnormalities** (*expert reading*) will be described: presence of portal thrombosis, hepatic venous thrombosis, biliary tract invasion, and visualization of arterio-portal fistula.
- **Number of nodules detected** (*ongoing on-site and expert reading*)
- **Qualitative evaluation** (*expert reading*)
 - At each phase (T2, T1 unenhanced, arterial, portal, delayed, 15 ±5 minutes): nodule (maximum of 3) intensity relative to parenchyma according to the scale: hypointense, hyperintense or isointense (and relative to spleen on T2 if hyperintense); In addition nodules will be described as homogeneous or heterogeneous
 - Presence of fat and Iron within the liver nodules at unenhanced phase in and opposed phase (intra nodule)
 - Visualization of a perilesional capsule (yes/no) at portal phase or delayed phase or at 15 ±5 minutes
- **Quantitative evaluation** (*ongoing on-site reading*)
 - At each phase, (T1 unenhanced, arterial, portal, delayed, 15 ±5 minutes) SI measurement on nodule (maximum of 3), liver, and background for SNR, CNR, and nodule percentage enhancement (PE)

Nodule SNR (Signal to noise ratio) will be calculated at each phase using the following formula: $SInodule/SDnoise$ where $SInodule$ is “nodule ROI intensity” and $SDnoise$ is “Background ROI: SD intensity”.

CNR (contrast to noise ratio) will be calculated at each phase using the following formula: $(SInodule-SIIliver)/ SDnoise$ where $SInodule$ is “nodule ROI intensity”; $SIIliver$ is “liver parenchyma ROI intensity” and $SDnoise$ is “Background ROI: SD intensity”.

PE (Nodule Percentage Enhancement) will be calculated using the following formula: $[(SIp\text{post}-SIp\text{pre})/SIp\text{pre}]*100$ where $SIp\text{post}$ is the nodule signal intensity at each phase (arterial, portal, delayed, 15 ±5 minutes) and $SIp\text{pre}$ is the nodule signal intensity at unenhanced sequence.

- On arterial and on portal phase, SI measurement of the aorta and the portal vein maximum vessel enhancement for SNR calculation purpose.

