9. STUDY SCHEDULE AND PROCEDURES

9.1 Study Schedule

9.1.1 Screening Visit – Visit 1 – Day - 7 to Day 0

During this visit, the following tasks or assessments will be performed:

- A **written informed consent** will be obtained from the subject as described in [Section 14.3](#);
- The subject will be attributed an **Identification Number** as described in [Section 4.3](#);
- A **routine physical examination** (performed by a physician) including the examination of general appearance, skin, neck (including thyroid), eyes, ears, nose, throat, lungs, heart, abdomen, back, lymph nodes, extremities, vascular and neurological; Information indicating the global assessment (normal or abnormal (specify)) of the physical examination should be recorded on source documentation;
- A review and record of **concomitant treatments**;
- Recording of **demographic data** such as sex, age, measurement of height, ethnic origin (self-reported race/ethnicity).
- **Documentation of relevant medical history**/current medical condition present before signing the informed consent. The Investigator will also question on any possible previous contrast agents injection intolerance (type of agent : iodinated, gadolinium complex, barium, radiopharmaceutical, other specify) and report them in medical history;
- **Documentation of chronic liver disease history and status**: documentation supporting the diagnostic of chronic liver disease (biopsy, endoscopic, biological, ultrasound parameters, and elastography), aetiology of chronic liver disease (alcohol, HBV, HCV, non-alcoholic-NASH, other specify) and last evaluation of Child Pugh score ([see appendix 1](#)) available (including the date);
- **Documentation of suspected nodules** detection modality and date;
- **Examination results available for standard of reference diagnosis evaluation** per nodule before P03277 administration:
 - Liver map (according to Couinaud segmentation) identifying the localization of the nodule(s) (maximum of 3) for standard of reference
 - Size of the nodule (s) to be considered according to investigator's choice among the several imaging modalities

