 - Contrast enhanced imaging modalities used for characterization (CT and/or MRI), type of contrast agent used for MRI (extracellular, hepatospecific), date of acquisition and, for each of nodules if HCC typical hallmark is visualized according to EASL/EORTC criteria and in case of MRI using hepatospecific contrast agent, also if hyperintensity of parenchyma relative to the nodule is seen.
 - The more recent AFP measurements available and date
- **Biopsy or intervention for specimen surgery** scheduled for histology analysis. The planned date should be recorded.
- A **urine or serum pregnancy test** for all women of childbearing potential should be done and must be negative;
- **Verification of eligibility criteria**. Criteria relative to eGFR measurement may not be available at screening ;

 CONFIDENTIAL	Protocol No. GDX-44-008 Version No.4.0 including amendments 1 and 2 12 December 2017	Page 38 / 64
---	--	--------------

- Schedule of **blood sample collection for serum creatinine** dosage if applicable, in order to obtain the results and calculate eGFR at the time of inclusion at the latest;
- If done at screening, **blood samples for baseline hematology/biochemistry tests** will be collected according to central laboratory manual. If not done at screening, they have to be scheduled at inclusion visit (V2).
- Recording the subject screening visit in the CRF.

9.1.2 Inclusion Visit – Visit 2 – Day 0

Inclusion visit can be the same day as screening if all eligibility criteria can be verified the same day.

During this visit, the following tasks or assessments will be performed:

- **Verification of inclusion and non-inclusion criteria** by the Investigator; creatinine results for eGFR calculation should be available before P03277 administration.
- **A urine or serum pregnancy test** for female subject of childbearing potential will be performed prior to P03277 administration and must be negative (do not perform the test if a negative pregnancy test result performed within 24 h prior to the MRI is available);
- Any changes in **concomitant treatments** since the last visit will be documented;
- **Any AE** occurred since the last visit will be documented
- If not already done at screening, **blood samples for baseline haematology/biochemistry tests** will be collected according to central laboratory manual;
- Measurement of **body weight**;

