9.3 On Site on going Reading of Images

For each investigational site, a radiologist expert in liver diseases will be appointed for on-site readings and provide on-site on-going reading results.

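### The open-label site fixes the non-histology reference diagnosis the day after the P03277 MRI, although all its scheduled inputs are on file before injection

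*Protocol*

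**What the plan says.** Section 9.1.3 (Visit 3, Day +1) lists a proposed standard-of-reference diagnosis for each nodule, which "should be assessed according to available evaluations (excluding histology and P03277 images". The flow chart agrees. Its row "Proposed diagnosis according to available examinations for standard reference (excluding histology and P03277 images" is marked only in the Day +1 column.

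The inputs come earlier. Section 9.1.1 has the reference examinations recorded "per nodule before P03277 administration", including "for each of nodules if HCC typical hallmark is visualized according to EASL/EORTC criteria" and the latest AFP with its date. The flow-chart row "Previous imaging results and AFP measurement collected for reference diagnosis" is marked at screening and at inclusion on Day 0, both ahead of dosing.

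Section 7.1 leaves the reference to the site, under its standard of care and adapted EASL/EORTC criteria. It gives three routes to HCC: positive histology, typical features on two triphasic modalities, or AFP above 200 ng/mL with a single nodule. Histology at Visit 4 is optional (9.1.4). Section 3.1 describes the study as open label.

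**The concern.** The reference label sets the denominators of the primary sensitivity and specificity (section 12.3, Table 2). It should be formed without knowledge of the test it will judge. Here it is formed a day after the site has acquired the P03277 images, by an unmasked site, with an instruction as the only safeguard. If knowledge of the P03277 MRI tips a borderline nodule into or out of HCC, the reference is no longer independent of the index test, and the resulting error cannot be separated from true diagnostic performance. Where histology is absent, this Day +1 call is the only scheduled reference diagnosis.

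**Working it through.** The protocol states no figure on this point, so there is none to reproduce. The check has two parts: the timeline, and the effect of one changed call.

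**1. Does waiting until Day +1 add anything?**

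- CT/MRI findings and hallmark per nodule: documented at Visit 1 (9.1.1).
- AFP: collected at Visit 1 or Day 0 (9.1.1, flow chart). It is not in the Day +1 laboratory panel (7.2.2).
- New imaging with another agent: excluded, since section 6.3 says "Any other contrast agent should not be administered with 7 days before and 3 days after P03277 administration".
- Histology: expressly left out of this call.
- P03277 MRI: Day 0 (9.1.2).

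The only nodule information that the schedule adds between the last input and the Day +1 call is the P03277 examination itself.

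**2. Can the site know the P03277 result by then?** Under section 9.3, "a radiologist expert in liver diseases will be appointed for on-site readings and provide on-site on-going reading results". Section 7.2.1 makes that reading include "SI measurement on nodule (maximum of 3), liver, and background for SNR, CNR, and nodule percentage enhancement (PE" at the arterial, portal and delayed phases, which are the phases that define the HCC hallmark. The protocol does not say whether this reading precedes the Day +1 call, or whether one person does both. Exposure is therefore possible but not certain.

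**3. Effect of one changed call, cohort 1.** Assumptions: one nodule per subject and no decisive histology. Section 8 gives 30 subjects and about 66% HCC: 30 × 0.66 = 19.8, taken as 20 HCC and 10 not HCC. Section 1 gives 0.820 and 0.934 for extracellular agents in lesions of any size: 20 × 0.82 = 16.4, taken as 16, and 10 × 0.934 = 9.34, taken as 9. Hence n1 = 16, n3 = 4, n2 = 1, n4 = 9.

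Sensitivity = n1/(n1+n3); specificity = n4/(n2+n4).

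| Reference call changed | Sensitivity | Specificity |
|---|---|---|
| None | 16/20 = 80.0% | 9/10 = 90.0% |
| Site agrees with experts: a false negative becomes not HCC | 16/19 = 84.2% | 10/11 = 90.9% |
| Site agrees with experts: a false positive becomes HCC | 17/21 = 81.0% | 9/9 = 100% |
| Site disagrees with experts: a true negative becomes HCC | 16/21 = 76.2% | 8/9 = 88.9% |
| Site disagrees with experts: a true positive becomes not HCC | 15/19 = 78.9% | 9/11 = 81.8% |

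The exact 95% interval for 16/20 is 56.3% to 94.3%, so the sensitivity shifts lie within sampling error.

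**4. Direction.** The index result is the later expert reading, by consensus if the two readers differ (7.1, 9.4.5), and not the site's impression. Let every nodule be open to drift at the same rate d, and let site and experts agree on P03277 with the same probability a for all nodules. Of the 30 nodules, 5 are scored wrong and can become right; 25 are scored right and can become wrong. The net change in correct calls is d × [5a − 25(1 − a)] = d × (30a − 25). It is positive only if a > 25/30 = 83%. Inflation is thus not guaranteed.

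**5. Other settings.**

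- Cohort 2: 10 × 0.66 = 6.6, taken as 7 HCC and 3 not HCC, with 6/7 and 3/3 correct assumed. One call moves sensitivity from 85.7% to between 6/8 = 75.0% and 6/6 = 100%. Specificity falls at most to 3/4 = 75.0%.
- Cohort 1 with three nodules per subject (60 HCC, 30 not HCC; 49/60 and 28/30 correct): one call moves sensitivity from 81.7% to between 49/61 = 80.3% and 49/59 = 83.1%.
- Histology: if half the nodules have a decisive result, 15 of 30 remain exposed.

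**The case against.** The protocol excludes the P03277 images from this call in two places that agree. The HCC rule is written down, its imaging and AFP inputs are recorded beforehand, and Table 2 merges every other category with uncertain, so the primary split is mostly a rule applied to data already on file. Section 12.3 tabulates those inputs, so an HCC label without a supporting route could be found afterwards. Table 1 gives nodule diagnosis to the expert readers only, and the timing of the on-site reading may be settled in the Site Imaging Manual. The calculation shows what one relabelled nodule does to any small table; it does not estimate bias. The study is exploratory and runs no test.

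Most of this is fair and limits the point: this is a risk, not a contradiction, and its size is unknown. Three things remain. An instruction not to use images is weaker than not yet having them. The reference to local standard of care and adapted criteria leaves judgement-based calls that the 12.3 tables cannot check. Sampling error being larger does not excuse a bias that can be avoided.

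A further objection is that a standard-of-care AFP result returned after injection could not be used if only histology may update the call. That is true but narrow, since the flow chart collects AFP for the reference only at screening and inclusion. When screening and injection fall on the same day, the site does have somewhat more to complete before dosing.

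**Conclusion.** The concern holds. The schedule puts the non-histology reference call after the index MRI at an open-label site, and the delay adds no scheduled input. The drift rate is unknown, so only the effect per changed call can be given: in cohort 1, under the assumptions above, up to about 4 points of sensitivity either way and between 8 points down and 10 points up in specificity. It is larger in cohort 2, and about 1.5 points of sensitivity in cohort 1 if each subject has three nodules. Only HCC versus not-HCC/uncertain calls on nodules without decisive histology are at risk. The change is worth making because it protects the independence of the primary reference at very little cost; nothing here shows that the results would be materially wrong without it.

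**What to change.** In section 9.1.3 and the flow chart, move the proposed reference diagnosis based on imaging and AFP from Visit 3 to Visit 1 or Visit 2. Lock it in the CRF, with date and time, before P03277 is injected. Afterwards let only histology update it, and keep the earlier call on record so that any change can be seen.

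The cost is one CRF item moved to an earlier visit, one flow-chart edit and slightly more site work before injection. No scheduled input is lost, and no extra staff, procedure or table is needed.

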9.1.4 Visit 4 – Optional (from 3 days up to 13 weeks)

Optionally, a biopsy will be done or surgically resected specimen will be collected at the time of loco-regional treatment and be analyzed for histology by local pathologist.

This procedure, whatever the type (biopsy or surgery), should be done between 3 days after P03277 administration to up to 13 weeks maximum. Alternatively it is acceptable to record results from histology done within 2 months prior to P03277 administration.

- **Examination results available for standard of reference diagnosis evaluation**
 - Date of nodule material collection (2 dates maximum)
 - Histological diagnosis per nodule : HCC, other malignant, regenerative or dysplastic nodule, benign, uncertain
- **Assessment of AEs that the investigator considers related to P03277 and/or study procedures.**

9.2 Imaging Protocol

1.5 T and 3T MR equipments will be accepted. The same machine for each site should be used all along the study. Automatic real time bolus tracking will be used.

Standard Axial MR sequences will be used for pre-injection and post injection imaging.

- **Unenhanced imaging sequences:**
 - GRE T1 in- and opposed-phase sequence
 - 3D GRE T1 sequence with fat saturation
 - FSE T2 sequence with fat saturation (can be done after injection)
- **Contrast-enhanced imaging sequences** - Post P03277 injection:
 - 3D GRE T1 sequences with fat saturation acquired during 3 time-points at arterial (bolus track synchronization), portal (approx. 70-80 sec post injection) and delayed (3 minutes post

 CONFIDENTIAL	Protocol No. GDX-44-008 Version No.4.0 including amendments 1 and 2 12 December 2017	Page 40 / 64
--	--	--------------

injection) phases

- 3D GRE T1 sequences with fat saturation acquired at 15 ± 5 minutes
- Additional 3D GRE T1 sequences with fat saturation will be performed at 20mn, 1hour and 2 hours post-injection for the first 5 subjects and then possibly proposed to next subjects if significant liver parenchyma enhancement is depicted.

9.3 On Site on going Reading of Images

For each investigational site, a radiologist expert in liver diseases will be appointed for on-site readings and provide on-site on-going reading results.

9.4 Expert Reading of Images

9.4.1 Manuals and Supplies

Guerbet will document the imaging tasks and obligations of the investigational site in a Site Imaging Manual. The standardized image acquisition guidelines will be provided to the sites as part of the Site Imaging Manual.

In addition, the Site Imaging Manual will detail the steps required for masking confidential subject information and transferring images to Guerbet.

Guerbet will document the expert imaging process in a Read Charter.

9.4.2 Site Qualification

Guerbet's monitors will perform pre-study site selection and site training. These contacts will ensure that the imaging protocol-stipulated can be performed by the site, are programmed and prepared prior to enrollment of the first subject and that the Site Imaging Manual will be accurately followed by the investigator.

9.4.3 Receipt, Tracking, Quality Check of Images

During the study, Guerbet will request that investigational sites send anonymous images of the subjects to Guerbet. Their format will be agreed prior to study start and defined in the Site Imaging Manual. Images will be tracked within Guerbet.

Guerbet will ensure that all imaging protocol requirements have been followed and will document this quality control.

9.4.4 Expert Readers training

Two expert radiologists will be appointed from the participating sites, having expertise in the interpretation of MR images from of liver diseases and HCC.

Before the expert readers start the readings, proper training will be delivered and documented according to the Read Charter.

Reading software at each site will be recorded.

9.4.5 Image assessments

After having received all the subject images acquired with P03277 for the study, Guerbet will be presenting them to expert readers.

A specific CRF will be set-up for experts reading entry.

 CONFIDENTIAL	Protocol No. GDX-44-008 Version No.4.0 including amendments 1 and 2 12 December 2017	Page 41 / 64
---	--	--------------

Both experts will provide evaluation for qualitative evaluations of P03277 imaging according to the Read Charter.

9.4.6 *Nodule mapping*

Nodule tracking will be performed using a liver map according to Couinaud segmentation drawings completed on-site and by expert readers. The purpose is to guarantee an unambiguous assignment (matching) of the liver nodules between standard of reference and expert readings. Read charter will detail how nodule mapping will be organized.

9.4.7 *Consensus meeting*

In case of diagnostic discordance (primary criterion), a consensus meeting will be organized after nodule concordance. In this case the qualitative evaluations will be reviewed globally and may be modified.

9.4.8 *Image Warehouse and Final Deliverables*

All imaging data will be maintained in a secure environment. Guerbet will maintain a centralized image archive that will contain every imaging examination received from the clinical investigators for the study. Measurements will also be stored at reader site responsible for quantitative evaluation so that these data may be audited if necessary.

